### **11.3 REPORTING TO HEALTH AUTHORITIES**

Adverse event reporting to regulatory agencies will be done by the MAH according to local and international regulatory requirements.

## **12. PLANS FOR DISSEMINATING AND COMMUNICATING STUDY RESULTS**

The progress reports and final reports will be submitted to PMDA in Japan PSR (Periodic safety report). And also the interim report for this PMS is included in re-examination documents.

This study is planned for the publication based on the final report.

## **ANNEX 1. LIST OF STAND-ALONE DOCUMENTS**

None

## **ANNEX 2. ENCePP CHECKLIST FOR STUDY PROTOCOLS**

### **ENCePP Checklist for Study Protocols (Revision 3)**

Adopted by the ENCePP Steering Group on 01/07/2016

The European Network of Centres for Pharmacoepidemiology and Pharmacovigilance (ENCePP) welcomes innovative designs and new methods of research. This Checklist has been developed by ENCePP to stimulate consideration of important principles when designing and writing a pharmacoepidemiological or pharmacovigilance study protocol. The Checklist is intended to promote the quality of such studies, not their uniformity. The user is also referred to the ENCePP Guide on Methodological Standards in Pharmacoepidemiology, which reviews and gives direct electronic access to guidance for research in pharmacoepidemiology and pharmacovigilance.

For each question of the Checklist, the investigator should indicate whether or not it has been addressed in the study protocol. If the answer is "Yes", the section number of the protocol where this issue has been discussed should be specified. It is possible that some questions do not apply to a particular study (for example, in the case of an innovative study design). In this case, the answer 'N/A' (Not Applicable) can be checked and the "Comments" field included for each section should be used to explain why. The "Comments" field can also be used to elaborate on a "No" answer.

This Checklist should be included as an Annex by marketing authorisation holders when submitting the protocol of a non-interventional post-authorisation safety study (PASS) to a regulatory authority (see the Guidance on the format and content of the protocol of non-interventional post-authorisation safety studies). The Checklist is a supporting document and does not replace the format of the protocol for PASS as recommended in the Guidance and Module VIII of the Good pharmacovigilance practices (GVP).

**Study title:**

Specific Use-Result Surveillance of Spiriva Respimat in asthmatics (patients with mild to moderate persistent asthma)

**Study reference number:**

BI Study Number: 0205-0536

Section 1: Milestones	Yes	No	N/A	Section Number
1.1 Does the protocol specify timelines for				
1.1.1 Start of data collection 				6
1.1.2 End of data collection 				6
1.1.3 Study progress report(s)				6
1.1.4 Interim progress report(s)				6
1.1.5 Registration in the EU PAS register				6
1.1.6 Final report of study results.				6

Comments:

none

 Date from which information on the first study is first recorded in the study dataset or, in the case of secondary use of data, the date from which data extraction starts.

 Date from which the analytical dataset is completely available.

Section 2: Research question	Yes	No	N/A	Section Number
2.1 Does the formulation of the research question and objectives clearly explain:				
2.1.1 Why the study is conducted? (e.g. to address an important public health concern, a risk identified in the risk management plan, an emerging safety issue)				7
2.1.2 The objective(s) of the study?				8
2.1.3 The target population? (i.e. population or subgroup to whom the study results are intended to be generalised)				9.2
2.1.4 Which hypothesis(-es) is (are) to be tested?				
2.1.5 If applicable, that there is no a priori hypothesis?				

Comments:

--

Section 3: Study design	Yes	No	N/A	Section Number
3.1 Is the study design described? (e.g. cohort, case-control, cross-sectional, new or alternative design)				9
3.2 Does the protocol specify whether the study is based on primary, secondary or combined data collection?				9
3.3 Does the protocol specify measures of occurrence? (e.g. incidence rate, absolute risk)				9
3.4 Does the protocol specify measure(s) of association? (e.g. relative risk, odds ratio, excess risk, incidence rate ratio, hazard ratio, number needed to harm (NNH) per year)				
3.5 Does the protocol describe the approach for the collection and reporting of adverse events/adverse reactions? (e.g. adverse events that will not be collected in case of primary data collection)				11

Comments:

none

Section 4: Source and study populations	Yes	No	N/A	Section Number
4.1 Is the source population described?				
4.2 Is the planned study population defined in terms of:				6
4.2.1 Study time period?				9.3
4.2.2 Age and sex?				
4.2.3 Country of origin?				9.3

Section 4: Source and study populations	Yes	No	N/A	Section Number
4.2.4 Disease/indication? 4.2.5 Duration of follow-up?				9.3
4.3 Does the protocol define how the study population will be sampled from the source population? (e.g. event or inclusion/exclusion criteria)				9.2

Comments:

none

Section 5: Exposure definition and measurement	Yes	No	N/A	Section Number
5.1 Does the protocol describe how the study exposure is defined and measured? (e.g. operational details for defining and categorising exposure, measurement of dose and duration of drug exposure)				9.3
5.2 Does the protocol address the validity of the exposure measurement? (e.g. precision, accuracy, use of validation sub-study)				
5.3 Is exposure classified according to time windows? (e.g. current user, former user, non-use)				
5.4 Is exposure classified based on biological mechanism of action and taking into account the pharmacokinetics and pharmacodynamics of the drug?				

Comments:

none

Section 6: Outcome definition and measurement	Yes	No	N/A	Section Number
6.1 Does the protocol specify the primary and secondary (if applicable) outcome(s) to be investigated?				9.3
6.2 Does the protocol describe how the outcomes are defined and measured?				9.3
6.3 Does the protocol address the validity of outcome measurement? (e.g. precision, accuracy, sensitivity, specificity, positive predictive value, prospective or retrospective ascertainment, use of validation sub-study)				
6.4 Does the protocol describe specific endpoints relevant for Health Technology Assessment? (e.g. HRQoL, QALYs, DALYs, health care services utilisation, burden of disease, disease management)				

Comments:

none

Section 7: Bias	Yes	No	N/A	Section Number
-------------------------------	------------	-----------	------------	-----------------------

Section 7: Bias	Yes	No	N/A	Section Number
7.1 Does the protocol describe how confounding will be addressed in the study?				
7.1.1. Does the protocol address confounding by indication if applicable?				
7.2 Does the protocol address:				
7.2.1. Selection biases (e.g. healthy user bias)				
7.2.2. Information biases (e.g. misclassification of exposure and endpoints, time-related bias)				
7.3 Does the protocol address the validity of the study covariates?				

Comments:

none

Section 8: Effect modification	Yes	No	N/A	Section Number
8.1 Does the protocol address effect modifiers? (e.g. collection of data on known effect modifiers, sub-group analyses, anticipated direction of effect)				

Comments:

none

Section 9: Data sources	Yes	No	N/A	Section Number
9.1 Does the protocol describe the data source(s) used in the study for the ascertainment of:				
9.1.1 Exposure? (e.g. pharmacy dispensing, general practice prescribing, claims data, self-report, face-to-face interview, etc.)				
9.1.2 Outcomes? (e.g. clinical records, laboratory markers or values, claims data, self-report, patient interview including scales and questionnaires, vital statistics, etc.)				
9.1.3 Covariates?				
9.2 Does the protocol describe the information available from the data source(s) on:				
8.2.1 Exposure? (e.g. date of dispensing, drug quantity, dose, number of days of supply prescription, daily dosage, prescriber)				9.3
8.2.2 Outcomes? (e.g. date of occurrence, multiple event, severity measures related to event)				9.3
8.2.3 Covariates? (e.g. age, sex, clinical and drug use history, co-morbidity, co-medications, life style, etc.)				9.3
9.3 Is a coding system described for:				
9.3.3 Exposure? (e.g. WHO Drug Dictionary, Anatomical Therapeutic Chemical (ATC) Classification System)				
9.3.2 Outcomes? (e.g. International Classification of Diseases (ICD)-10, Medical Dictionary for Regulatory Activities (MedDRA))				9.7
				

Section 9: Data sources	Yes	No	N/A	Section Number
9.3.3 Covariates?				
9.4 Is a linkage method between data sources described? (e.g. based on a unique identifier or other)				

Comments:

none

Section 10: Analysis plan	Yes	No	N/A	Section Number
10.1 Is the choice of statistical techniques described?				
10.2 Are descriptive analyses included?				9.7
10.3 Are stratified analyses included?				
10.4 Does the plan describe methods for adjusting for confounding?				
10.5 Does the plan describe methods for handling missing data?				9.7
10.6 Is sample size and/or statistical power estimated?				9.5

Comments:

none

Section 11: Data management and quality control	Yes	No	N/A	Section Number
11.1 Does the protocol provide information on data storage? (e.g. software and IT environment, database maintenance and anti-fraud protection, archiving)				9.10
11.2 Are methods of quality assurance described?				9.10
11.3 Is there a system in place for independent review of study results?				9.10

Comments:

none

Section 12: Limitations	Yes	No	N/A	Section Number
12.1 Does the protocol discuss the impact on the study results of:				
12.1.1 Selection bias?				9.9
12.1.2 Information bias?				
12.1.3 Residual/unmeasured confounding? (e.g. anticipated direction and magnitude of such biases, validation sub-study, use of validation and external data, analytical methods)				

Section 12: Limitations	Yes	No	N/A	Section Number
12.2 Does the protocol discuss study feasibility? (e.g. study size, anticipated exposure, duration of follow-up in a cohort study, patient recruitment)				

Comments:

none

Section 13: Ethical issues	Yes	No	N/A	Section Number
13.1 Have requirements of Ethics Committee/ Institutional Review Board been described?				
13.2 Has any outcome of an ethical review procedure been addressed?				
13.3 Have data protection requirements been described?				

Comments:

none

Section 14: Amendments and deviations	Yes	No	N/A	Section Number
14.1 Does the protocol include a section to document amendments and deviations?				5

Comments:

none

Section 15: Plans for communication of study results	Yes	No	N/A	Section Number
15.1 Are plans described for communicating study results (e.g. to regulatory authorities)?				12
15.2 Are plans described for disseminating study results externally, including publication?				12

Comments:

none

Name of the main author of the protocol: \_\_\_\_\_

Date: 16/Dec/2016

Signature: \_\_\_\_\_

### ANNEX 3. FLOW CHART OF VARIABLES

#### 1. Observation period

Item \ Time	Observation period 		
	Before first administration of Spiriva Respimat	4W	12W (or at discontinuation)
Patient registration	X 		
Patient demographics	X		
Administration of Spiriva Respimat	X (to be recorded throughout the observation period)		
Medical history/baseline conditions	X		
Previous/concomitant therapies	X (to be recorded throughout the observation period)		
Pulmonary function test			
FEV 1	(X)	(X)	(X)
FVC	(X)	(X)	(X)
PEFR 	(X)	(X)	(X)
Asthma severity	X		
Asthma Control Status	(X)	(X)	(X)
QOL (ACQ 6 score)	(X)	(X)	(X)
Adverse events	X (to be recorded throughout the observation period)		
Laboratory tests  associated with AE		(X)	
EDC transmitted time 		X	

(X): If applicable

- 1: Time points during the observation period are approximate. Collected data should be reported as of the closest available visit.
- 2: Patients administered Spiriva Respimat will be registered within 14 days from whenever the day of first administration is possible.
- 3: PEFR is defined as the mean of the PEFR values of the 7 days before each visit.
- 4: When laboratory related AE is reported, Laboratory tests associated with AE are reported.
- 5: eCRF (electronic case report form): Data are to be transmitted immediately after being entered into the eCRF at 12 weeks after the start of treatment or at discontinuation. In case of occurrence of any adverse events, the data should be immediately entered into the eCRF and transmitted.

## 2. LIST OF ABBREVIATIONS

---

Term	Definition / description
ACQ	Asthma Control Questionnaire
ADS	Analysis Data Set
AE	Adverse event
BMI	Body mass index
CI	Confidence Interval
CRF	Case Report Form
EMA	European Medicines Agency
FEV 1	Forced Expiratory Volume in one second
FVC	Forced Vital Capacity
ICS	Inhaled Corticosteroids
LABA	Long Acting $\beta$ 2 Agonist
LTRA	Leukotriene Receptor Antagonist
MedDRA	Medical Dictionary for Regulatory Activities
NIS	Non-interventional Study
OCS	Oral Corticosteroid
PEFR	Peak Expiratory Flow Rate
PFT	Pulmonary Function Test
PMS	Post-Marketing Surveillance
PT	Preferred term
PV	Protocol violation
Q1	Lower quartile
Q3	Upper quartile
RMP	Risk Management Plan
SABA	Short Acting $\beta$ 2 Agonist
SAMA	Short Acting Muscarinic Antagonist
SD	Standard deviation
SMQ	Standardised MedDRA query
SOC	System organ class
TOC	Table of contents
TSAP	Trial statistical analysis plan

---

### **3. INTRODUCTION**

The purpose of this document is to provide a more technical and detailed elaboration of the principal features of the analysis described in the protocol, and to include detailed procedures for executing the statistical analysis of the post-marketing surveillance (PMS) data.

This TSAP assumes familiarity with the Non-interventional Study (NIS) Protocol, including Protocol Amendments. In particular, the TSAP is based on the planned analysis specification as written in NIS Protocol Section 9.7 “DATA ANALYSIS”. Therefore, TSAP readers may consult the NIS Protocol for more background information on the study, e.g., on study objectives, study design and population, treatments, definition of measurements and variables, planning of sample size.

SAS® Version 9.4 will be used for all analyses.

#### **4. CHANGES IN THE PLANNED ANALYSIS OF THE STUDY**

No change has been made in the planned analyses from the statistical methods described in the NIS Protocol.

## **5. ENDPOINT(S)**

### **5.1 PRIMARY ENDPOINT(S)**

The primary endpoints will be used as defined in the NIS Protocol Section 9.3.2.1.

### **5.2 SECONDARY ENDPOINT(S)**

#### **5.2.1 Key secondary endpoint(s)**

This section is not applicable as no key secondary endpoint has been specified in the protocol.

#### **5.2.2 Secondary endpoint(s)**

The secondary endpoints will be used as defined in the NIS Protocol Section 9.3.2.2.

### **5.4 OTHER VARIABLE(S)**

#### **Demographic data and baseline characteristics:**

- Sex: male, female
- Age [years]  
Age [years] = Actual age based on the first administration of Spriva Respimat
- Height [cm]
- Body mass index (BMI) [kg/m^2]  
 $BMI [kg/m^2] = \text{weight [kg]} / (\text{height [m]})^2$
- Smoking status: Never smoked, Ex-smoker, Current smoker, Unknown
- Pack-Years
- Indication for use: Bronchial asthma, Other
- Asthma Severity: Severe persistent, Moderate persistent, Mild persistent, Intermittent, Unknown
- Duration of asthma [years]

Duration of Spiriva Respimat treatment [days] = (date of last drug intake) – (date of first drug intake) + 1 – (period of treatment interruption [days])

- Total Spiriva Respimat dose taken [µg]
- First dose of Spiriva Respimat [µg]: 2.5, 5.0, Others

Table 5.4: 1 ICS doses of ICS product

Agent	Low dose (µg/day)	Medium dose (µg/day)	High dose (µg/day)
BDP-HFA	=< 200	> 200 to 400	> 400
FP-HFA	=< 200	> 200 to 400	> 400
CIC-HFA	=< 200	> 200 to 400	> 400
FP-DPI	=< 200	> 200 to 400	> 400
MF-DPI	=< 200	> 200 to 400	> 400
BUD-DPI	=< 400	> 400 to 800	> 800
FF-DPI		100 to <200	>= 200

BDP-HFA, beclometasone dipropionate hydrofluoroalkane;

FP-HFA, fluticasone hydrofluoroalkane; CIC-HFA, ciclesonide hydrofluoroalkane;

FP-DPI, fluticasone propionate dry powder inhaler;

MF-DPI, mometasone furoate dry powder inhaler; BUD-DPI, budesonide dry powder inhaler.

Table 5.4: 2 ICS doses of ICS/LABA combination product

Agent	Low dose (µg/day)	Medium dose (µg/day)	High dose (µg/day)
FP/SM	=< 200	> 200 to 500	> 500
BUD/FM	=< 320	> 320 to 640	> 640
FP/FM	=< 200	> 200 to 500	> 500
FF/VI		100 to <200	>= 200

FP, fluticasone propionate; SM, salmeterol xinafoate; BUD, budesonide;

FM, formoterol fumarate; FF, fluticasone furate; VI, vilanterol trifenate.

## **6. GENERAL ANALYSIS DEFINITIONS**

### **6.1 TREATMENT(S)**

For basic information on treatment in the study, please refer to NIS Protocol Section 4. The technical specification for treatment set-up is described in the Analysis Data Set (ADS) plan.

For safety analyses analyses, data up to 30 days after last treatment intake will be considered as on treatment.

### **6.2 IMPORTANT PROTOCOL VIOLATIONS**

The following table defines the different categories of important PVs. The final column describes which PVs will be used to exclude patients from the different patient analysis sets. Observed PVs will be concluded as important or not important at report planning meetings before database lock at the latest.

Table 6.2: 1 Important protocol violations

Category/ Code	Description	Example/Comment	Method	Excluded from
A	Entrance criteria not met			
A1.1	Patient received Spiriva Respimat treatment before registration	Refer to Previous Medication code:	Automated	Safety
A1.2	Patients who have been enrolled this study before		Automated	Safety
B	Contract			
B1	No valid site contract was available		Manual	Safety
C	Trial medication			
C1	No treatment with Spiriva Respimat		Automated	Safety
D	Missing data			
D1	No patient visit after registration	No visit made after the entry	Automated	Safety
D2	No CRF after registration		Automated	Safety
D3	No safety observation was documented after registration	No AE details	Automated	Safety
D4	No value at baseline and/or at post treatment	None of value about asthma control status, PEFR, FEV 1 , FVC and ACQ6 for effectiveness analysis, at baseline and/or at post treatment	Automated	Effective ness
E	Invalid registration			
E1	No required registration procedure was followed	See the NIS Protocol Section 9.2.2.2	Manual	Safety

### 6.3 SUBJECT SETS ANALYSED

The following two analysis sets are defined as in NIS Protocol Section 9.7. The safety set will be the basis of all demographic, baseline and safety analyses. Effectiveness analysis will be on basis of the effectiveness set.

- **Safety set:**  
This patient set includes all patients who were documented to have taken at least one dose of Spiriva Respimat except for patients who had no observation documented after entry, made invalid registration or were not under the appropriate site contact.
- **Effectiveness set:**  
This patient set is a subset of the safety set that includes all patients in the safety set who have baseline and at least one available on-treatment asthma control status, PEFR, FEV1, FVC or ACQ 6 score.

Table 6.3: 1 Subject sets analysed

Class of endpoint	Subject set	
	Safety Set	Effectiveness Set
Primary endpoints	X	
Secondary and further endpoints		X
Demographic and baseline characteristics	X	
Treatment exposure	X	

## **6.5 POOLING OF CENTRES**

This section is not applicable because centre/country is not included in the statistical model.

## **6.6 HANDLING OF MISSING DATA AND OUTLIERS**

Safety:

Missing or incomplete AE dates are imputed according to BI standards (see “Handling of missing and incomplete AE dates”).[\(3\)](#)

Effectiveness:

Missing effectiveness data will not be imputed.

## **6.7 BASELINE, TIME WINDOWS AND CALCULATED VISITS**

With regard to effectiveness and safety endpoints, the term “baseline” refers to the last observed measurement prior to administration of Spiriva Respimat.

Effectiveness analyses will be performed based on calculated visits as shown in [Table 6.7: 1](#). If two or more data points of a patient fall into the same interval, the closest value to the planned day will be selected. If there are two observations which have the same difference in days to the planned day or if there are two observations on the same day, the first value will be used.

Table 6.7: 1 Baseline, time windows and calculated visits

Week label	Planned days	Time window (actual days on treatment)	
		Start	End
Baseline	0	The last observed measurement prior to administration of Spiriva Respimat	
Week 4	28	1	56
Week 12	84	57	111

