### 9.2.3 Study visits

After start of the treatment with Spiriva Respimat, each patient will be observed for 12 weeks or at premature discontinuation from the PMS. Observations are made at the following time points: before first administration of Spiriva Respimat (this visit is defined as baseline), 4 weeks and 12 weeks after the start of treatment, or at discontinuation.

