#### 9.3.2.2 Secondary outcome

- Change from baseline in asthma control status at Week 12

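### The SAP's day windows keep an asthma control status recorded at discontinuation on day 56 or earlier out of the Week 12 secondary outcome, although the protocol collects it in the Week 12 column

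*SAP*

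**What the plan says.** Protocol Section 9.3.2.2 names one secondary outcome, "Change from baseline in asthma control status at Week 12". Section 9.2.3 schedules post-baseline observations at "4 weeks and 12 weeks after the start of treatment, or at discontinuation". The flow chart in Annex 3 gives the last of these a single column, headed "12W (or at discontinuation". Its footnote 1 calls the time points approximate and adds: "Collected data should be reported as of the closest available visit".

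SAP Section 6.7 states: "Effectiveness analyses will be performed based on calculated visits as shown in" Table 6.7: 1. That table has three rows: baseline, Week 4 (planned day 28, days 1 to 56) and Week 12 (planned day 84, days 57 to 111). There is no row or rule for an assessment at discontinuation. For competing values the SAP says: "If two or more data points of a patient fall into the same interval, the closest value to the planned day will be selected". Ties go to the first value.

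Other SAP provisions decide what happens next:
- Section 6.6: "Missing effectiveness data will not be imputed".
- Section 7.5.2 assesses effectiveness at each visit and classes a missing status as Unknown.
- Section 6.3 admits to the effectiveness set any patient in the safety set with a baseline and at least one on-treatment value of a listed measure. A Week 12 value is not required.
- Section 7 takes percentages, unless otherwise specified, over the whole patient set including patients with missing values. It also provides listings of individual effectiveness values.

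**The concern.** Sites are asked for a final asthma control status from patients who stop early, and the flow chart collects it in the Week 12 column. The analysis then sorts by day, so a status from a patient who stops in the first eight weeks cannot inform the only effectiveness outcome that the protocol names. No later effectiveness assessment is scheduled for that patient, and nothing is imputed.

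If some of these patients stop because control has worsened, their worsening is recorded but appears at Week 12 only as Unknown. The Week 12 share classed as Worse is then too low, and a reader of the table cannot tell an early stopper from a patient who simply has no Week 12 value.

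**Working it through.** **1. Reproduce the windows.** Planned days are 28 and 84 (SAP Table 6.7: 1). The midpoint is (28 + 84)/2 = 56, so Week 4 ends on day 56 and Week 12 starts on day 57. The Week 12 window is symmetric: 84 - 27 = 57 and 84 + 27 = 111. These match the table.

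**2. Apply the selection rule.** Hypothetical patients, with distance from day 28 deciding within days 1 to 56:

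| Week 4 visit (day) | Discontinuation (day) | Week 4 value from | Week 12 value from | Discontinuation value |
|---|---|---|---|---|
| none | 10, 20 or 40 | discontinuation | none | used as Week 4 |
| 14 | 35 | day 35 (7 < 14) | none | used as Week 4 |
| 10 | 29 | day 29 (1 < 18) | none | used as Week 4 |
| 28 | 45 or 56 | day 28 (0 < 17 or 28) | none | in no visit summary |
| 42 | 50 | day 42 (14 < 22) | none | in no visit summary |
| 30 | 57 | day 30 | day 57 | used as Week 12 |
| 28 | 70 | day 28 | day 70 | used as Week 12 |

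No discontinuation value on day 56 or earlier reaches Week 12. It drops out of the visit summaries only when another value in days 1 to 56 is closer to day 28, or equally close and earlier. A patient seen exactly on day 28 has distance 0, so any discontinuation value on days 29 to 56 loses.

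**3. Status at Week 12.** With no Week 12 value and no imputation, the patient is Unknown under SAP Table 7.5.2: 1. With a baseline and any on-treatment value, the patient stays in the effectiveness set and, by default, in the denominator.

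**4. Direction.** Let d be the share of the set stopping on day 56 or earlier with a status recorded at discontinuation. Let w_e be the share worse among them and w_c the share worse among the rest, all of whom are taken to have a Week 12 value.
- Worse with discontinuation values: (1 - d) w_c + d w_e.
- Worse under the default denominator: (1 - d) w_c. The shortfall is d w_e, above zero whenever any early stopper was worse.
- Worse among observed values only: w_c. The shortfall is d (w_e - w_c), above zero only if early stoppers worsened more often than the rest.

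The same algebra holds for Improved.

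**5. Illustration.** All inputs are assumed: 45% improved and 10% worse among patients with a Week 12 value; 15% improved and 50% worse among early stoppers; d = 10% or 20%.

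| | d = 10% | d = 20% |
|---|---|---|
| Worse, default denominator | 0.9 x 10 = 9% | 0.8 x 10 = 8% |
| Worse, observed only | 10% | 10% |
| Worse, with discontinuation values | 9 + 0.1 x 50 = 14% | 8 + 0.2 x 50 = 18% |
| Improved, default denominator | 0.9 x 45 = 40.5% | 0.8 x 45 = 36% |
| Improved, observed only | 45% | 45% |
| Improved, with discontinuation values | 40.5 + 0.1 x 15 = 42% | 36 + 0.2 x 15 = 39% |
| Unknown, default denominator | 10% | 20% |

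The shortfall in Worse is 5 to 10 points under the default denominator and 4 to 8 among observed values. If early stoppers worsened no more often than the rest (w_e = 10%), it is 1 to 2 points (0.1 x 10 and 0.2 x 10) and zero respectively.

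The documents cannot replace these assumptions. Enrolling 180 to secure 150 (Protocol Section 9.5) allows a loss of 30/180 = 16.7% from the safety set, which is not a discontinuation rate.

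**The case against.** The strongest defence is that sorting by day is legitimate and the SAP hides nobody. Much of it stands.

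- A reader might infer that early discontinuation values are discarded. They are not, as a rule: step 2 shows that many become the Week 4 value, which is also assessed, and the SAP provides listings of individual values.
- A reader might infer that Week 12 is purely a completer result. It is not: patients who stop on day 57 or later and are assessed then count, and earlier stoppers in the effectiveness set remain visible as Unknown in the default denominator.
- A reader might infer that the windows flatter the drug throughout. In the illustration, Improved is understated under the default denominator. It is overstated only among observed values.
- The link between discontinuation and Week 12 rests on the Annex 3 column heading. The outcome itself is defined at Week 12, Section 9.2.3 lists discontinuation as an alternative time point, and footnote 1 partly supports mapping by day. That footnote concerns approximate timing, however, and does not say that a discontinuation assessment becomes Week 4.
- A reader might infer that the SAP Section 4 statement, "No change has been made in the planned analyses from the statistical methods described in the NIS Protocol", is untrue. The documents do not support that: it concerns statistical methods, and Protocol Section 9.7 contains no visit-mapping rule to change.
- The published SAP skips Sections 5.3, 6.4 and 7.6, so a further summary in text not shown cannot be ruled out.

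What none of this removes is the effect of Table 6.7: 1 itself. A status recorded at discontinuation on day 56 or earlier cannot enter the Week 12 outcome, and the published text gives no rule for it.

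**Conclusion.** The point holds in this limited form: the protocol's combined Week 12 or discontinuation slot and the SAP's day windows do not match, and the mismatch removes early discontinuation assessments from the Week 12 outcome. Under the default denominator, Worse at Week 12 is understated whenever an early stopper was worse at discontinuation. Among observed values, that requires early stoppers to have worsened more often than the rest.

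The true size is unknown. The 5 to 10 point figure is an illustration under the assumed splits, and it would stand beside a displayed Unknown share. The study is descriptive, with no confirmatory test and no primary effectiveness outcome, so no formal conclusion is at risk. The change is still worth making, because it is cheap and this is the only effectiveness outcome the protocol names.

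**What to change.** Keep the observed Week 12 result as it is. Add one supplementary row to SAP Table 6.7: 1, Week 12 or discontinuation, defined as the Week 12 window value if present and otherwise the assessment made at discontinuation. State that Week 4 values are not carried forward for patients who only missed Week 12, so that the no-imputation rule in Section 6.6 is respected.

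In Section 7.5.2, tabulate change in asthma control status at this time point beside the Week 12 result, with the number of patients contributed by discontinuation. Split the Week 12 Unknown category into patients who discontinued before day 57 and all others.

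The cost is SAP wording, one derived visit and one extra table. No new data are needed, since Annex 3 already schedules the assessment where applicable. The drawback is that the supplementary time point mixes assessment times, which is why it accompanies the Week 12 result and does not replace it.
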